1.3. Rationale for This Study

There is a significant unmet medical need for a safe, convenient, and effective treatment for RSV infection. The only approved antiviral therapy for RSV, ribavirin, is approved for use in pediatric populations only, but is rarely used in clinical practice due to its limited efficacy and concerning safety profile. There is no approved antiviral therapy for RSV infection among HCT recipients, where the current standard of care is supportive.

This study follows a Phase 1 FIH study (GS-US-218-0101) and a Phase 2a RSV challenge study (GS-US-218-0103), which evaluated the safety, tolerability, and PK of single and multiple doses of presatovir in 140 healthy adult volunteers. In Study GS-US-218-0103, presatovir was shown to be efficacious in reducing RSV viral load and clinical symptoms in healthy adult subjects experimentally infected with RSV.

Given these results from healthy adult volunteers studied in a controlled setting, the current study is designed to evaluate the safety, tolerability, PK, and efficacy of presatovir among HCT patients with an RSV related URTI. Safety and efficacy data generated from this study, taken together with currently available data will be used to support further clinical development of presatovir in pediatric and adult patients infected with RSV.

1.4. Dose Rationale

The dose and administration schedule selected for this study is a single dose of 200 mg presatovir administered orally or via NG tube on Days 1, 5, 9, 13, and 17. This regimen was selected based upon the PK characteristics of presatovir and the pharmacokinetic/pharmacodynamic (PK/PD) relationship established in the antiviral effect study with different doses/regimens in Study GS-US-218-0103.

In Study GS-US-218-0103, a 5-day treatment regimen of presatovir (50 mg single dose on Dose Day 1, followed by 25 mg once daily on Dose Days 2 through 5) resulted in a significant reduction in RSV viral load. The mean AUC of RSV viral load as measured by the RT-qPCR assay from first viral load measurement post initial dose of study drug through end of quarantine (Day 12) was significantly lower in presatovir subjects compared to placebo subjects ($\Delta = 506.9 \log_{10} \text{PFUe} \cdot \text{hour/mL}$, $p < 0.001$). This 5-day regimen was able to achieve presatovir trough concentrations ~4-5 fold of paEC_{95} (52 ng/mL) for up to 120 hours following dose initiation for the virus used in the challenge study, the M37 strain of RSV.

In selecting the dose for the current study, the goal was to achieve presatovir trough concentrations above 4-fold of paEC_{95} for 95% of of the clinical RSV isolates for the duration of RSV shedding in HCT patients. Longitudinal viral dynamics data from investigators at an academic HCT center also indicate that the majority of HCT patients shed RSV for 15 days, but some may shed for as long as 21 days (unpublished). In addition, recent studies indicate that the mean time to progression of URTI to LRTI is 7 days, with 90% of subjects progressing within 15 days after presenting with a URTI {[Shah et al 2013](#)}, {[Kim et al 2014](#)}. Therefore, a total of 5 doses of presatovir (200 mg each dose, every 4 days) is expected to provide > 4-fold paEC_{95} coverage for ~95% of 75 wild-type clinical RSV isolates through Day 22, which is expected to result in significant durable antiviral effect.

1.5. Compliance

This study will be conducted in compliance with this protocol, Good Clinical Practice (GCP), and all applicable regulatory requirements.

2. OBJECTIVES

The co-primary objectives of this study are:

- To evaluate the effect of presatovir on RSV viral load and development of LRTC in RSV-positive autologous or allogeneic HCT recipients with acute URTI symptoms

The secondary objectives of this study are:

- To evaluate the effect of presatovir on progression to respiratory failure or all-cause mortality
- To evaluate the PK, safety, and tolerability of presatovir

3. STUDY DESIGN

3.1. Endpoints

The co-primary endpoints of this study are:

- Time-weighted average change in nasal RSV viral load (\log_{10} copies/mL) from Baseline (Day 1) to Day 9 as measured by RT-qPCR
- Proportion of subjects who develop a LRTC through Day 28, defined as one of the below, as determined by the adjudication committee:
 - Primary RSV LRTI
 - Secondary bacterial LRTI
 - Lower respiratory tract infection due to unusual pathogens
 - Lower respiratory tract complication of unknown etiology

The secondary endpoint of this study is the proportion of subjects developing respiratory failure (of any cause) requiring mechanical ventilation (invasive or noninvasive) or all-cause mortality through Day 28.

The exploratory endpoints of this study are:

- PPD [REDACTED]
- [REDACTED]
- [REDACTED]
- [REDACTED]
- [REDACTED]
- [REDACTED]
- [REDACTED]
- [REDACTED]

PPD [Redacted]

[Redacted]

[Redacted]

[Redacted]

[Redacted]

[figure not shown]
[Redacted]

[Redacted]

[Redacted]

3.2. Study Design

This is a randomized, double-blind, placebo-controlled study evaluating the effect of presatovir on efficacy, PK, safety, and tolerability in HCT recipients with RSV URTI. This study will enroll approximately 200 subjects from approximately 80 international HCT centers. RSV positive subjects with URTI symptoms and no evidence of LRTI will be randomized 1:1 to receive presatovir or placebo administered as 200 mg every 4 days for 5 doses. Subjects will be followed for a total of 28 days, during which a total of 10 Study visits will be performed to follow safety, tolerability, PK, and viral loads in nasal samples and the blood. PPD [Redacted]

3.3. Study Treatments

Approximately 200 subjects will be randomized 1:1 to receive 200 mg (four 50 mg tablets) of IMP (presatovir or placebo) as a single dose on Days 1, 5, 9, 13, and 17. The IMP will be administered orally or via NG tube. The entire dose must be taken within 1 hour. Investigational medicinal product should be dispensed with gloves.

Subjects will remain in the clinic for 30 minutes post-dose for observation. If vomiting occurs within 30 minutes after IMP administration and undissolved tablets are present in the vomitus, the subject should receive another dose. If another dose is administered, the subject should remain in the clinic for an additional 30 minutes post-dose for observation.

Presatovir will be provided as white, plain-faced, film-coated, round tablets containing 50 mg presatovir (61 mg GS-5806-02, bis-hydrochloride salt dihydrate form of presatovir). Placebo to Match will be provided as white, plain-faced, film-coated, round tablets containing no presatovir.

The expected duration of subject participation is approximately 1 month, to include Screening through the final visit on Day 28.

3.4. Duration of Treatment

The treatment portion of the study is 17 days (a total of 5 doses administered as single doses on Days 1, 5, 9, 13, and 17).

3.5. Discontinuation Criteria

Reasons for potential premature discontinuation from IMP dosing include:

- Any Grade 3 or 4 AE or SAE
- Intercurrent illness that would, in the judgment of the investigator, affect the subject's ability to receive IMP (eg, unable to ingest oral dose)
- ALT, AST $> 5 \times$ ULN and rising
- ALT, AST remains $> 5 \times$ ULN with no change in TB for more than 2 weeks
- A worsening of clinical symptoms with no other acceptable explanation
- Hy's Law criteria are met:
 - Evidence of injury: elevation of the ALT or AST by $> 3 \times$ ULN; and
 - Evidence of dysfunction: elevation of the TB by $> 2 \times$ ULN without an elevation of the alkaline phosphatase (ALP) by $> 2 \times$ ULN; and
 - Clinical verification to ensure effect is health product-induced and not induced by disease or another cause of injury

In the event that any of the above criteria are met, the Principal Investigator (PI) will review the case in detail and discuss with the Gilead Medical Monitor whether the subject should be discontinued from IMP. If close monitoring of ALT, AST, ALP, and TB per Section 6.11.6 is not possible, IMP will be discontinued.

Reasons for premature discontinuation from the Study include:

- Subject request to discontinue for any reason
- Subject noncompliance
- Pregnancy during the study; refer to Section 7.7.2
- Discontinuation of the study at the request of Gilead, a regulatory agency or an institutional review board or independent ethics committee (IRB/IEC)

If a subject prematurely discontinues from IMP dosing, he/she will remain on study and will continue with all subsequent Study Visits and assessments, with the exception of IMP dosing.

If a subject prematurely discontinues from the study, every attempt should be made to bring the subject back for the Early Termination procedures. See Section 6.9.2 for more information.

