6.9.1. Assessments for Premature Discontinuation from IMP Administration

If a subject prematurely discontinues IMP dosing, the subject will remain on study and will continue with all subsequent study visits and assessments through Visit 10, Day 28/End of Study Visit, with the exception of IMP administration.

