6.9.2. Assessments for Early Termination/Withdrawal

Every attempt should be made to keep subjects in the study and to perform the required study-related and follow-up procedures (see Sections 6.2 through 6.7). If this is not possible or acceptable to the subject or investigator, the subject may be withdrawn from the study.

If a subject withdraws early from the study for any reason, every attempt should be made to bring the subject back to the clinic or hospital for the following early termination assessments:

- FLU-PRO questionnaire (only if the subject withdraws prior to Visit 6 [Day 9])
- Vital Signs (body temperature, heart rate, respiratory rate, and blood pressure)
- O₂ saturation (on room air)
- Weight
- Blood sample collection for central and local laboratory analysis:
 - Safety Labs (hematology and serum chemistry to include to include WBC with differential, Hgb, platelets, BUN, creatinine, serum albumin, AST, ALT, ALP, and TB)
 - Serum antibody titer to RSV
 - Respiratory syncytial virus viremia
 - Pharmacokinetic sampling (only if the subject withdrawals prior to Visit 9 [Day 22])
 - Local troponin testing
- Nasal samples (2 total, 1 from each nostril)
- 12-lead ECG
- Assessment of AEs, concomitant medications, hospitalizations, re-hospitalizations, ICU admissions or utilization of ICU care > 24 hours, standard of care test results (ie, chest radiographs, microbiology, echocardiograms), mechanical ventilation (invasive and non-invasive of any duration), and supplemental O₂ use (≥ 2 L/min for > 24 hours)

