6.11.9. Collection of Standard of Care Clinical Data for Central Review

6.11.9.1. LRTC Source Documentation for Adjudication Committee Review

During the course of the study, it is anticipated that Investigators will perform chest X-rays and/or CT scans as part of standard of care if there is any concern of a lower respiratory tract complication. Images and results for chest X-rays used for screening and eligibility, including the comparison chest X-ray, and all scans done as part of standard of care (to include CT and chest X-rays) while subjects are on study, will be collected and stored electronically for review by the Adjudication Committee and a possible central read. Additionally, the following results from any confirmatory testing will be collected:

- Results of all local microbiology tests performed while on study through Visit 10 or early termination before Visit 10 (All bacterial, viral, fungal, parasite, or other results from samples obtained from any respiratory specimen [eg, bronchoalveolar lavage, sputum, pleural fluid, lung tissue] and from blood specimens, including bacterial culture, viral PCR, and serology studies).
- Echocardiogram tracings and reports of any ECG performed in relation to a potential LRTC event
- Temperature

- Clinical notes (with range of dates)
- Daily body weights
- Autopsy reports (if performed)
- Other supporting documentation, as requested

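### Protocol 3.5 and 6.9.2 let a still-consenting subject be taken off study, and 6.11.9.1 then ends routine collection of the scans and microbiology needed to adjudicate LRTC through Day 28; the expected effect is small

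*Protocol*

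**What the plan says.** Protocol 3.5 separates stopping drug from leaving the study. For stopping drug the rule is clear: "If a subject prematurely discontinues from IMP dosing, he/she will remain on study and will continue with all subsequent Study Visits and assessments". Section 6.9.1 repeats it: "the subject will remain on study and will continue with all subsequent study visits and assessments through Visit 10". The drug-only list already holds most of the clinical reasons, including Grade 3 or 4 AEs, SAEs, worsening symptoms and illness ("Intercurrent illness that would, in the judgment of the investigator").

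The second list in 3.5 opens with "Reasons for premature discontinuation from the Study include". Apart from subject request and a stop by the sponsor, a regulator or an IRB/IEC, it contains "Subject noncompliance" and pregnancy. No definition or threshold for noncompliance appears in either document.

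Section 6.9.2 first asks sites to try to keep subjects, then adds: "If this is not possible or acceptable to the subject or investigator, the subject may be withdrawn from the study". For those who leave, "every attempt should be made to bring the subject back to the clinic or hospital for the following early termination assessments". That visit covers standard-of-care results, hospitalizations and ventilation up to that date.

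Section 6.11.9.1 sets what reaches the adjudicators. Standard-of-care scans are gathered for the time a subject is on study. The microbiology item reads: "Results of all local microbiology tests performed while on study through Visit 10 or early termination before Visit 10". Other documents may be requested.

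**The concern.** LRTC through Day 28 is a co-primary endpoint, and adjudication depends on clinical notes, radiology and microbiology (Protocol 8.10). A subject removed for noncompliance or pregnancy, or because the investigator finds continued participation unacceptable, may still consent and may still be treated at the transplant centre. The outcome could be ascertained, but the routine flow of evidence stops at exit.

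Removal does not take the subject out of the primary analysis. The FAS needs only one full dose and a quantifiable Day 1 sample (SAP 3.1.2). Missed doses and swabs exclude a subject only from the Per Protocol set (SAP 3.1.3). Noncompliance is therefore already handled in the analysis, and removing the subject gains nothing there while it can create an avoidable unknown outcome.

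**Working it through.** **1. The rules side by side.**
- Drug stopped for any reason (3.5, 6.9.1): all visits continue through Visit 10.
- Subject unblinded and drug stopped (5.1.1): the paragraph ends by committing to follow all subjects to completion unless the subject specifically withdraws consent.
- Pregnancy (Appendix 5, item 5): stop study drug. Nothing there says to leave the study, whereas 3.5 lists pregnancy as a study-level reason.
- Noncompliance, or the investigator's view (3.5, 6.9.2): the subject may be taken off study with consent intact.

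The last rule and the 3.5 pregnancy entry are out of line with the others.

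**2. What safety reporting still catches.** Section 7.3 covers SAEs and deaths within 4 weeks or 30 days of the last dose. The shortest case is a subject dosed only on Day 1: 1 + 28 = Day 29, or 1 + 30 = Day 31. Both pass Day 28. Hospitalization is an SAE criterion (7.1.2), and Section 1.1 says LRTI often leads to it. What remains exposed is mainly a later LRTC that meets no SAE criterion, plus later imaging and microbiology.

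**3. The plan's own power.** Inputs from Protocol 8.8: 30% vs 10%, 100 per arm, two-sided alpha 0.04 (z = 2.054). Pooled-variance test, mean proportion 0.20:

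power = Φ{[0.20 − 2.054·√(0.32/n)] / √(0.30/n)}

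Here 0.32 = 2 × 0.20 × 0.80 and 0.30 = 0.30 × 0.70 + 0.10 × 0.90. At n = 100: (0.20 − 0.1162)/0.0548 = 1.53, so power is 93.7%. This agrees with the stated figure of over 90%.

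**4. Assumed removal.** The documents give no rate. Assume 2% to 5% of the 189 enrolled (SAP 1.3), equal in both arms:
- Per arm: 0.02 × 189/2 = 1.89; 0.05 × 189/2 = 4.73.
- Upper bound on LRTC events lost, if removal precedes any event and nothing is recovered: placebo 1.89 × 0.30 = 0.57 to 4.725 × 0.30 = 1.42; presatovir 1.89 × 0.10 = 0.19 to 4.725 × 0.10 = 0.47.
- Removal at Day 9 (8 elapsed days), exponential with the 7-day mean in Section 1.4: exp(−8/7) = 0.319. Placebo 0.18 to 0.45; presatovir 0.06 to 0.15. The exponential is tolerable: 1 − exp(−15/7) = 88.3%, against the stated 90% within 15 days.

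**5. Power after removal** (removed subjects excluded, same formula):

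| Base | No removal | 2% removed | 5% removed |
|---|---|---|---|
| All 189 in FAS (94.5 per arm) | 92.3% | 91.8% | 91.0% |
| FAS 90% of 189, assumed (85.05 per arm) | 89.4% | 88.7% | 87.7% |

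The loss due to removal is 92.3 − 91.8 = 0.5 points at the least and 89.4 − 87.7 = 1.7 points at the most. Counting removed subjects as non-events gives much the same: at 100 per arm, 93.7% falls to 93.1% (2%) or 92.1% (5%).

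**6. Unequal loss, illustration only.** If 5% of events were missed in placebo alone, 28.5% vs 10% at 94.5 per arm gives 88.6%. Nothing in the documents points to such an imbalance.

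**The case against.** The best defence has four parts.

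- **5.1.1 already states the right principle.** Its last sentence speaks of all subjects. It closes a paragraph about unblinded subjects, however, so its scope is arguable. Read narrowly, it does not reach 3.5 and 6.9.2; read generally, it contradicts them. Either way the text needs aligning.
- **Little is left to lose.** The SAE and death window spans Day 28 for every dosed subject, the early termination visit recovers events up to exit, and further documents can be requested. This stands, and it is why the point is small. It does not restore the adjudication package as a matter of routine, nor does it capture a non-serious LRTC.
- **The numbers rest on an unsourced rate.** True. With all 189 in the FAS and 5% removed, power is 91.0%, still over 90%. In the smaller-FAS scenario power is already 89.4% before any removal, so that shortfall is not due to this rule.
- **It is late.** SAP 1.3 records that enrolment was halted on 20 September 2017, and the SAP revision is dated 10 October 2017. An amendment would reach few subjects still inside 28 days. That limits the benefit in this trial but does not make the protocol text sound.

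A reader might also infer that the SAP has no way to handle unknown LRTC status. The documents do not establish that. SAP 3.6.1 gives a discontinuation rule for viral load and a general rule against imputation, and no LRTC-specific rule is visible. But SAP 6.5 is redacted, the adjudication charter is not available, and an FAS sensitivity table for this endpoint is listed (15.9.1.2.3), though it may be only the covariate regression in SAP 6.2.2.

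**Conclusion.** The point holds as a wording defect worth correcting: the protocol permits avoidable missing data on a co-primary endpoint in subjects who remain in the FAS. The expected size is small, about 0.5 to 1.7 points of LRTC power, on an assumed equal removal of 2% to 5% and, for the upper end, an assumed FAS of 90% of those enrolled. SAE reporting would recover some of the events counted as lost. The secondary endpoint (ventilation or death) is less exposed, since those events are largely caught by SAE and death reporting. The pregnancy entry is a minor alignment.

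Two stronger readings are not supported. One is that sick or deteriorating subjects are forced off study: removal is optional, and illness, severe AEs and worsening symptoms are on the drug-only list. The other is that the result is biased towards or against presatovir: neither a removal rate nor a difference between arms can be derived from the documents.

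**What to change.** 1. **Section 3.5:** delete noncompliance from the study-discontinuation list, and move pregnancy to the drug-discontinuation list to match Appendix 5.
2. **Section 6.9.2:** allow withdrawal from the study only when the subject withdraws consent, or when the sponsor, a regulator or an IRB/IEC stops the study. State that noncompliance or missed doses may stop drug only, with all scheduled visits still attempted through Visit 10 as in 6.9.1. The wording should not let missed doses end visits, since that would weaken 6.9.1 and could cost nasal samples for the viral-load endpoint.
3. **Section 6.11.9.1:** collect standard-of-care scans, microbiology, ventilation and vital status through Day 28 for every dosed subject unless consent is withdrawn.

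The cost is an amendment to three sections, with IRB/IEC approval (9.2.1) across about 80 planned centres, and some record retrieval for subjects who attend poorly. No visit or imaging is added; the only chest X-ray the protocol requires remains the one at Screening (6.11.7).

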3.6. Source Data

For the purposes of this study, study specific questionnaires (ie, respiratory symptom assessments) are considered source documents and are to be filed with the subject's medical or study records. Electronic data (ie, diagnostic machines that transcribe data directly to a database, or data entered directly into an Electronic Medical Record system) is considered source data, provided the data is not recorded directly on the CRF/eCRF, and provided there is a clear audit trail in the electronic record(s). Template source document worksheets will be prepared by Gilead and provided to sites to use at their discretion. If source document worksheets are used, they are to be kept with the subject's medical or study records as original source documents. No data will be recorded directly on the CRF/eCRF, and any data recorded directly on the CRF/eCRF will not be considered source data.

4. SUBJECT POPULATION

4.1. Number of Subjects and Subject Selection

The subject population will consist of approximately 200 RSV-positive adult male and female subjects 18 to 75 years of age who have had an allogeneic or autologous HCT and have documented acute RSV related URTI symptoms, recruited from approximately 80 centers in Asia Pacific, Canada, Europe, Japan, South America, and the United States.

4.2. Inclusion Criteria

Subjects must meet all of the following inclusion criteria to be eligible for participation in this study.

- 1) Adult male and female subjects 18 to 75 years of age. In Japan subjects must be 20 to 75 years of age. In Singapore subjects must be 21 to 75 years of age.
- 2) Received an autologous or allogeneic HCT using any conditioning regimen
- 3) Documented to be RSV-positive as determined by local testing (eg, PCR, DFA, RVP assay, or culture) using an upper respiratory tract sample collected ≤ 6 days prior to Day 1, or as determined at Screening as per Section 6.1.1
- 4) New onset of at least 1 of the following respiratory symptoms for ≤ 7 days prior to Day 1: nasal congestion, runny nose, cough, or sore throat, or worsening of one of these chronic (associated with a previously existing diagnosis, eg, chronic rhinorrhea, seasonal allergies, chronic lung disease) respiratory symptoms ≤ 7 days prior to Day 1
- 5) No evidence of new abnormalities consistent with LRTI on a chest X-ray relative to the most recent chest X-ray, as determined by the local radiologist. If a chest X-ray is not available or was not obtained during standard care < 48 hours prior to Screening, a chest X-ray must be obtained for Screening
- 6) O_2 saturation $\geq 92\%$ on room air
- 7) An informed consent document signed and dated by the subject or a legal guardian of the subject and the investigator or his/her designee. In Sweden ICFs signed by a legal guardian must also be signed by a close relative of the subject.
- 8) A negative urine or serum pregnancy test is required for female subjects (unless surgically sterile or greater than two years post-menopausal)
- 9) Male and female subjects of childbearing potential must agree to contraceptive requirements as described in [Appendix 5](#)
- 10) Willingness to complete necessary study procedures and have available a working telephone or email

